### 2.4. Study Plan

Patients will undergo a screening period (up to 12 weeks), a double-blind treatment period of 24 weeks (Part B), a 28-week extended active treatment period (Part C), and a 12-week follow-up period as depicted in [Figure 2](#). All patients will be followed up for an additional 12 weeks after completing Part C. Patients in Parts B who choose not to participate in or are ineligible for Part C will be followed for an additional 12 weeks immediately after Part B.

**Figure 2: Study Flow Diagram for Part B and Part C**

DB = double-blind.

Note: For patients who do not have at least 11 daily entries during the 14 days immediately preceding the planned randomization date (baseline), randomization should be postponed until this requirement is met, but without exceeding the 85-day maximum duration for screening.

After adult patients provide informed consent and adolescent patients and/or their legal parents/legal guardians provide informed consent and informed assent (as appropriate), patients will be assessed for study eligibility at visit 1.

Study participants are required to have a confirmed diagnosis of EoE which may be established *either* by a prior historical biopsy showing  $\geq 15$  intraepithelial eosinophils per high-power field (eos/hpf) from at least one esophageal region after at least 8 weeks of treatment with a high-dose proton pump inhibitor (PPI) *or* by biopsies performed after approximately 8 weeks of high-dose PPI treatment initiated prior to screening or during the screening period, which demonstrate  $\geq 15$  intraepithelial eos/hpf in at least 2 out of 3 esophageal regions (proximal, mid, and distal); see Protocol Figure 3 for endoscopy/biopsy procedure flow chart. Patients who are on PPIs during the screening period and are eligible to enroll in the study must continue a high-dose PPI regimen during the study (see details in Protocol Section 7.2). Patients are allowed to switch among the approved background therapy options for high-dose PPI use during the study.

All patients who meet the other clinical and laboratory eligibility criteria will undergo endoscopy with biopsies at visit 2 (day  $-21 \pm 7$ ) both to establish a baseline reference measure and to ensure eligibility. For patients without a historical biopsy, the visit 2 biopsy will serve as both confirmation of EoE diagnosis and the baseline reference measure.

All biopsies performed during this study will be evaluated by pathologists at a central pathology laboratory who will be blinded to treatment assignment.

Note: Biopsy specimens from the stomach and/or duodenum will be obtained in all patients  $< 18$  years of age to rule out alternate etiologies of esophageal eosinophilia. Targeted, stomach and/or duodenal biopsies will be obtained in adults only in the event of abnormal endoscopic findings (other than typical EoE findings) or clinical suspicion of alternate etiologies. All randomized patients found to have stomach and/or duodenal abnormalities at baseline will have follow-up stomach and/or duodenal biopsies at week 24 and week 52.

After confirmation of EoE diagnosis, patients will be given an electronic diary (eDiary) to record dysphagia symptoms on a daily basis during the 2 weeks prior to the baseline visit (visit 3).

Patients may be re-screened once if they fail the screening evaluation, unless the reason for screen failure is related to histologic or clinical disease severity inclusion criteria. The baseline endoscopy with biopsy and EoE-EREFS scoring will not be repeated for re-screened patients. These results will continue to be valid baseline data. Re-screening must occur within 6 months of the screen failure.

For patients whose DSQ diary compliance does not meet eligibility requirements within the 21-day interval between Visit 2 and Visit 3 (at least 11 daily entries during the 14 days immediately preceding the planned randomization date), randomization may be postponed as long as the total duration of the screening period does not exceed the 85-day maximum.

At the baseline visit (visit 3), patients who continue to meet eligibility criteria will enter the 24-week, placebo-controlled, double-blind treatment period and be randomized in a 1:1:1 ratio to dupilumab 300 mg SC QW, dupilumab 300 mg SC Q2W or placebo SC. Randomization will be stratified by age ( $\geq 18$  vs.  $\geq 12$  to  $< 18$  years of age) and use of PPI at randomization (yes vs. no).

During the 24-week, placebo controlled, double-blind treatment period, clinic visits are scheduled per the schedule of events (Section 11.2). Patients and parents/caregivers will be trained on injecting study drug at the first 3 visits during the double-blind treatment period. Patients will be closely monitored at the study site at visits 3 to 6 (baseline visit, study weeks 1, 2, and 4) for a minimum of 30 minutes after the administration of study drug. During weeks when no clinic visit is scheduled, the patient or parent/caregiver will administer study drug. Doses of study drug administered at home should be administered one week after the prior dose of study drug. Study drug administration that occurs in clinic should occur per the Schedule of Events in Section 11.2. Patients and parents/caregivers who prefer to have clinic staff administer study drug may choose to have injections administered in the clinic.

The end of treatment visit for the double-blind treatment period is at week 24. The co-primary endpoints will be assessed at week 24, one week after the last dose of study drug during the double-blind treatment period.

Patients who prematurely discontinue study treatment will be encouraged to remain in the study and attend all subsequent scheduled visits.

At the end of the double-blind treatment visit (week 24), eligible patients in Part B may enter Part C, which consists of a 28-week extended active treatment period. Patients from Part B who are randomized to placebo during the double-blind treatment period will be re-randomized in a 1:1 ratio to dupilumab 300 mg QW or dupilumab 300 mg Q2W. Patients randomized to dupilumab 300 mg Q2W will also receive matching placebo alternating with dupilumab doses so the injection frequency will be identical for both groups for regimen-blinding purposes. All other patients will remain on the same dupilumab dose regimen to which they are randomized during the double-blind treatment period. Patients who do not enter Part C may enter a 12-week follow-up period.

Due to the COVID-19 pandemic, the Sponsor allows study procedures to occur outside the protocol specified timepoint and/or outside of the clinic environment and will remain in effect only for the duration of the public health emergency:

- Endoscopy with biopsies may be delayed for visit 11/week 24, visit 19/week 52, early termination, and before initiating rescue treatment
- At-home study drug dosing is permitted for all visits except for visit 3/day 1 and visit 11/week 24
- If the for-cause endoscopy with biopsies cannot occur due to COVID-19 restrictions, rescue treatment should be initiated without delay and these patients will be eligible to participate in Part C
- Safety and laboratory procedures (vital signs, weight, PK/ADA sample collection, hematology and chemistry urine sample collection) may be delayed or occur at-home when possible
- The patient reported outcome questionnaires that are intended to be completed during clinic visits may be conducted via phone interviews after visit 3/day 1

Patients are allowed to extend their current assigned dose regimen of study drug (Parts B and/or C) until the post-baseline esophageal biopsy procedure(s) are performed.

### 3. ANALYSIS POPULATIONS

In accordance with guidance from the International Conference of Harmonization of Technical Requirements for Registration of Pharmaceuticals for Human Use (ICH) guideline ICH E9 Statistical Principles for Clinical Trials (ICH, 1998), the following population of analysis will be used for all statistical analysis.

The full analysis set (FAS) is the primary analysis population for Part B efficacy analyses. The Part B safety analysis set (SAF) is the basis for Part B safety analyses.

The Part C SAF is the basis for both efficacy and safety analyses of Part C.

#### 3.1. The Full Analysis Set (FAS)

The Part B full analysis set (FAS) includes all randomized patients in Part B. Efficacy analyses will be based on the treatment allocated by the IWRS at randomization (as randomized).

#### 3.2. The Safety Analysis Set (SAF)

##### Part B:

The Part B safety analysis set (SAF) includes all randomized patients who received any study drug in Part B; it is based on the treatment received (as treated). Treatment compliance/administration and all clinical safety variables in Part B will be analyzed using the Part B SAF.

##### Part C:

The Part C SAF includes all patients who were randomized in Part B, entered Part C, and received any study drug in Part C. Efficacy, treatment compliance/administration, and all clinical safety data from Part C through a pre-specified cut-off date around the time of Part B completion will be analyzed for Part C SAF patients who entered Part C from Part B.

The actual treatment group as treated for Part B is defined by the following rules:

- For a patient randomized to dupilumab 300 mg QW or dupilumab 300 mg Q2W, if the patient received all placebo injections in Part B, the actual treatment will be assigned as placebo.
- For a patient randomized to dupilumab 300 mg QW or dupilumab 300 mg Q2W, if the patient received at least one dupilumab injections in Part B, the actual treatment will be assigned as the planned treatment.
- For a patient randomized to placebo, if the patient received at least one dupilumab injections in Part B, the actual treatment will be assigned as dupilumab 300 mg Q2W.

The Part B treatment group assignment for analysis of Part C data will be the same as the SAF for Part B.

For safety summaries, the following analysis periods are defined:

- Part B week 24 treatment period is defined as
  - For patients who entered Part C: Day 1 to the date of first dose of Part C study drug (or week 24 visit if patient entered Part C but never received any Part C study drug).

- For patients who did not enter Part C:
  - Day 1 to the week 24 visit if patients completed week 24 visit with known visit date.
  - Day 1 to study day 169 (24 weeks times 7 days/week), or to patient’s last study participation date, whichever comes earlier, if patients did not complete week 24 visit or had missing week 24 visit date.
- Part C extended treatment period for patients who entered Part C is defined as
  - Time after the first dose of study drug in Part C to the date of week 52 visit if patients completed week 52 with known visit date.
  - Time after the first dose of study drug in Part C to study day 365 (52 weeks times 7 days/week), or to patient’s last study participation date, whichever comes earlier, if patients did not complete week 52 visit or had missing week 52 visit date.
- Follow-up period is defined as
  - For patients who entered Part C: the day after the end of Part C extended treatment period to the patient last study participation date.
  - For patients who did not enter Part C: the day after the end of Part B week 24 treatment period to the patient last study participation date.

The Part B and Part C SAFs will be the basis for the analyses for the Part B treatment period and Part C treatment period, respectively; however, for the analyses for the follow-up period, only a subset of the corresponding SAFs will be included, which is defined as the patients who entered the follow-up period and had at least one visit after week 24 visit (for Part B SAF) and week 52 visit (for Part C SAF).

Due to COVID-19 pandemic, patients are allowed to extend their current assigned dose regimen of study drug (Part B and/or Part C) until endoscopy with biopsy can be performed at week 24 visit and/or week 52 visit. The safety data during the extended dosing period will also be presented in the corresponding analysis period.

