### 2.1. Study Design and Randomization

Part B is a 24-week treatment, randomized, double-blind, placebo-controlled study phase to determine the treatment effect of dupilumab compared with placebo in adult and adolescent patients with EoE as assessed by histological and clinical measures. After a screening period up to 12 weeks, patients were centrally randomized via interactive web response system (IWRS) in a 1:1:1 ratio to dupilumab 300 mg SC QW, dupilumab 300 mg SC Q2W or placebo SC and treated double-blind for 24 weeks in Part B. Randomization was stratified by age ( $\geq 18$  vs.  $\geq 12$  to  $< 18$  years of age) and use of PPI at randomization (yes vs. no). At the end of Part B, eligible patients were to be provided an option to enter Part C, which consists of a 28-week period of active treatment with dupilumab. Patients from Part B who were randomized to placebo during the double-blind treatment period would be re-randomized in a 1:1 ratio to dupilumab 300 mg QW or dupilumab 300 mg Q2W. Patients from Part B who were randomized to dupilumab during the double-blind treatment period would remain on the same dupilumab treatment in Part C. Treatment assignment in Part C were managed by an interactive web response system (IWRS) to maintain blinding of treatment assignment in Part B. All patients would be followed up for an additional 12 weeks after completing Part C. Patients in Part B who do not enter Part C would enter a 12-week follow-up period immediately after Part B. Patients who participated in Part A were not eligible to participate in Part B.

Approximately 210 patients (70 per treatment group) are planned to be randomized in Part B from multiple global sites.

The design of the overall study is depicted below in [Figure 1](#). As Part A and Part B are carried out as 2 separate sub-studies with no overlap in patients, Part A and Part B will each have a separate 2-sided alpha level of 0.05.

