#### 5.7. Analysis of Safety Data

The analysis of safety and tolerability will be performed on the SAF, as defined in Section 3.2.

The safety analysis will be based on the reported AEs, clinical laboratory evaluations, vital signs and 12-lead ECG.

Thresholds for treatment-emergent Potential Clinically Significant Values (PCSVs) in laboratory variables, vital signs and ECG are defined in Section 11.3. Treatment-emergent PCSV is any PCSV developed or worsened in severity compared to the baseline during the treatment and follow-up period. When identifying treatment-emergent PCSVs in Part C, baseline is the last available valid measurement taken prior to the first dose of extended active treatment in Part C (scheduled to be administered at week 24 visit [visit 11]).

The time interval to detect any event or abnormality is between the first injection of study medication and EOS.

The summary of safety results will be presented for each study part by treatment received in the corresponding part. For safety variables/summaries involving baseline values, e.g., absolute change from baseline or shift table, study part specific baselines will be used. Summaries for Part B will use the study baseline (i.e., the latest available valid measurement prior to the first dose of study drug in the study). Summaries for Part C and follow-up period will use Part C baseline (i.e., the last available valid measurement prior to the first dose of extended active treatment in Part C).

In addition, the summary of safety results (including TEAEs, clinical laboratory, vital signs and ECG) will be performed for subjects who were impacted by COVID-19 pandemic and not impacted by COVID-19 pandemic in each study part, respectively.

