#### 5.7.1. Adverse Events

The number and proportion of patients reporting TEAEs will be summarized for Part B week 24 treatment period, Part C extended active treatment period, and follow-up period, as described in Section 3.2.

- For the summary of Part B treatment period, TEAEs with onset date during the Part B treatment period will be included. TEAEs that had an onset during the Part B treatment period and continued afterwards into Part C treatment period or the follow-up period will be counted only once as TEAEs during the Part B treatment period.
- For the summary of Part C extended treatment period, TEAEs with onset during the Part C extended treatment period will be included. TEAEs that had an onset during the Part C treatment period and continued afterwards into the follow-up period will be counted only once as TEAEs during the Part C extended treatment period.
- For the follow-up period, TEAEs with onset during the follow-up period will be included.

AE incidence tables will be presented by treatment group for the SAF as well as for selected subgroups. TEAE summaries will present the number (n) and percentage (%) of subjects experiencing an TEAE by SOC and PT, sorted by decreasing frequency of SOC and PT for the dupilumab treatment group. Multiple occurrences of AEs of the same PT (or SOC) in the same subject will be counted only once for that PT (or SOC). For tables presenting severity of events, the worst severity will be chosen for subjects with multiple instances of the same event. The denominator for computation of percentage is the number of patients in each treatment group for the corresponding analysis period as specified in Section 3.2.

An overall summary of TEAEs will be provided with number and proportions of patients with any:

- TEAE
- Serious TEAE
- TEAE of special interest (AESI)
- TEAE leading to death
- TEAE leading to permanent treatment discontinuation

Detailed summaries of TEAEs will include:

- TEAEs
  - TEAEs by SOC/PT
  - TEAEs by PT
  - TEAEs by SOC/PT with incidence of PT  $\geq 5\%$  in any treatment group
  - TEAEs by severity by SOC/PT
  - TEAEs related to study medication as assessed by the investigator by SOC/PT
  - TEAE of special interest by category (see Section 11.4)
- Serious TEAEs:
  - Serious TEAEs by SOC/PT
  - Serious TEAEs related to study medication as assessed by the investigator by SOC/PT
- TEAEs leading to permanent discontinuation of study treatment by SOC/PT
- Fatal TEAEs by SOC/PT

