  - a. If study drug administration is not possible in-clinic due to staff or patient availability due to COVID-19 restrictions, vital signs pre- and post-dose may not be performed.
14. For adolescent patients only.
15. Includes HIV Ab, HBsAg, HBsAb, HBcAb, HCV Ab, and TB. Tuberculosis testing will be performed on a country-by-country basis according to local guidelines if required by regulatory authorities or ECs.
16. Not required if post-menopausal status confirmed at screening. A negative result must be obtained prior to the randomization visit. In case of a positive urine test, the study treatment will be withheld and a serum pregnancy test to confirm the pregnancy should be performed as soon as possible. A confirmed pregnancy will lead to study drug discontinuation in all cases.
17. The EQ-5D-3L should be administered one time at either visit 1 or visit 3 for newly screened patients.
18. If COVID-19 restrictions limit the availability of staff or the patient to have in-clinic visits, the clinic staff should make every effort to contact the patient at the timepoint of the expected in-clinic visit to collect any AEs (including ISRs), any change in concomitant medications and/or procedures, and monthly pregnancy test results, if required.

Footnotes for Table 2

1. This visit is the same as the week 24 visit for Parts B (Table 6), and all other assessments indicated for week 24 of Parts B (Table 6) should be performed. All pre-dosing procedures (including endoscopy with biopsy) at visit 11/week 24 must be completed prior to administration of study drug for Part C extended active treatment.
2. Study assessments will be performed and blood samples will be collected prior to administration of study drug.
  - a. If COVID-19 restrictions limit the availability of staff or the patient to have in-clinic visits, procedures/sample collection should occur at the next available in-clinic visit. Pregnancy testing must be performed as indicated (in-clinic or at-home) monthly (at a minimum) and results reported in a timely manner.

3. Patients will be closely monitored at the study site at visits 11 (at a minimum) and 12, if possible, for a minimum of 30 minutes after the administration of study drug. In addition to predose assessments, AEs and vital signs (body temperature, blood pressure, respiratory rate, and heart rate) will be assessed at 30 minutes ( $\pm 10$  minutes) post-dose.

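### The Part B adverse-event period includes the whole date of the first Part C dose, so an event starting after that injection on the same date is tabulated in Part B, under placebo for former placebo patients

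*SAP*

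**What the plan says.** SAP 3.2 sets the safety periods. For Part B it gives "For patients who entered Part C: Day 1 to the date of first dose of Part C study drug". For Part C it gives "Time after the first dose of study drug in Part C to the date of week 52 visit" when week 52 was completed. Follow-up after Part C is "the day after the end of Part C extended treatment period to the patient last study participation date".

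SAP 5.7.1 assigns events to those periods. For the Part B table, "TEAEs with onset date during the Part B treatment period will be included". For the Part C table, "TEAEs with onset during the Part C extended treatment period will be included". The treatment label comes from SAP 5.7: "The summary of safety results will be presented for each study part by treatment received in the corresponding part".

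Part B placebo patients who enter Part C "would be re-randomized in a 1:1 ratio to dupilumab 300 mg QW or dupilumab 300 mg Q2W" (SAP 2.1). Their first Part C dose is given at visit 11, after the pre-dose procedures, which include endoscopy with biopsy. The footnotes to the Part C schedule (SAP 11.2) add: "Patients will be closely monitored at the study site at visits 11 (at a minimum) and 12, if possible". They require at least 30 minutes of observation and a post-dose check of adverse events and vital signs.

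Protocol 10.4.4.1 says that events occurring in Part C are summarized by the treatment received in Part C.

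**The concern.** The Part B cut is a calendar date, not the moment of the injection. The date of the first Part C dose contains time before the injection, which belongs to Part B, and time after it, which does not. The rule puts both in Part B.

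For patients already on dupilumab the treatment label stays right. For placebo patients switching to dupilumab it does not, because a reaction within minutes of a first dupilumab injection would be reported as a placebo event in the controlled comparison. The visit is one where such reactions are actively looked for, and the protocol (3.2.3.2) names systemic hypersensitivity as an important identified risk and reports more injection-site reactions with dupilumab. Elsewhere the SAP protects the placebo column: the as-treated rule in 3.2 moves a placebo patient who receives any dupilumab during Part B out of the placebo group. Exposure (SAP 5.5.2) is counted from the injections in each part, so the first Part C dose counts as Part C exposure while its same-day events count in Part B.

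**Working it through.** **1. Is the end date inclusive?** Follow-up begins the day after the preceding period ends, for patients who entered Part C and for those who did not. The last date therefore belongs to the period it closes, and the date of the first Part C dose belongs to Part B.

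**2. Apply the rules to three onsets around the first Part C injection.** The start of Part C can be read by clock time or by day.

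| Onset | Part B (by onset date) | Part C, read by clock time | Part C, read by day |
|---|---|---|---|
| Same date, before injection | yes | no | no |
| Same date, after injection | yes | yes | no |
| Next day | no | yes | yes |

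The first and third rows are correct. The second is in Part B on either reading. By clock time it meets both definitions, and no rule resolves the overlap; by day it is in Part B only.

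**3. Does another rule override this for adverse events?**
- SAP 6.4 excludes data collected after the first Part C injection from Part B, but as a heading to the visit windows. Its list of by-visit data does not include adverse events.
- The DSQ windows in 6.4 require a diary date strictly before the first Part C injection date. The SAP excludes that date when it means to; 3.2 does not.
- SAP 6.1 uses date and time for adverse events, but only to determine baseline.

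**4. Size.** The documents give no figure, so this is an illustration.
- Part B placebo arm: about 70 (SAP 2.1).
- Placebo patients entering Part C, n: not given. The 15% dropout assumption (SAP 2.3) suggests 70 × 0.85 = 59.5, about 60; range 50 to 70 (assumption).
- Probability r of a same-day post-dose event: not given; range 1% to 10% (assumption).

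Maximum rise in the placebo rate = n × r / 70:
- Low: 50 × 0.01 / 70 = 0.7 points
- Middle: 60 × 0.05 / 70 = 4.3 points (3 patients)
- High: 70 × 0.10 / 70 = 10.0 points

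If only the half assigned to QW receive dupilumab first:
- Low: 25 × 0.01 / 70 = 0.4 points
- Middle: 30 × 0.05 / 70 = 2.1 points
- High: 35 × 0.10 / 70 = 5.0 points

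**5. Effect on the contrast.** Same-day events in continuing dupilumab patients also enter Part B, under dupilumab. The shift in the contrast is therefore the placebo rise minus the dupilumab rise. With 60 entrants per arm and assumed rates of 5% (new to dupilumab) and 1% (continuing), it is 60 × 0.05 / 70 − 60 × 0.01 / 70 = 4.3 − 0.9 = 3.4 points. With equal entry and equal rates it is zero.

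**The case against.** The best case on the other side is that this is loose wording about one calendar day and the intent is visible. The visit-window headings cut Part B at the first Part C injection, the protocol reports Part C events by Part C treatment, and adverse-event times appear to be available. A sensible programmer might cut at the injection. That shows intent, but none of it governs the assignment of adverse events to periods, where the SAP's stated rule is onset date.

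Other parts of the objection stand, and they rule out stronger readings that a reader might infer.
- *That the events are also removed from the Part C table, so that two errors favour dupilumab.* Removal holds only if the Part C start is read by day; overlap holds only if it is read by clock time. Both cannot hold.
- *That the SAP resolves the overlap in favour of Part B.* The count-once sentence in 5.7.1 concerns events that start in Part B and continue into a later period. It is not a tie-break for an onset that meets both definitions.
- *That every re-randomized placebo patient is affected.* For those assigned Q2W with alternating placebo, the documents do not say which injection comes first.
- *That same-day injection-site reactions are all events of special interest.* Only severe or serious ones are, along with anaphylactic reactions and systemic hypersensitivity (SAP 4.5.1 and 11.4). Protocol 3.2.3.2 puts severe reactions, or those leading to discontinuation, below 2% of injection-site reactions. If all 3 patients in the middle case had such reactions, that is under 3 × 0.02 = 0.06.
- *That a single percentage-point figure describes the bias.* Patients are counted once per term, so one who already had that event in Part B adds nothing.

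**Conclusion.** The point holds as a misattribution in the stated rule. An event starting after the first Part C injection, on that date, is placed in Part B, and for a former placebo patient given dupilumab at that injection it is labelled placebo. This is certain only for patients re-randomized to QW and covers only onsets on that one date; later reactions go to Part C. Loss from the Part C table is possible but not established.

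The likely direction is to raise placebo rates and narrow the safety contrast, provided that same-day events are commoner in patients new to dupilumab than in those continuing it. The range of 0.7 to 10 points (about 0.4 to 5 if only QW assignees count) rests on assumed entry numbers and event rates. It is an upper bound on the change in the placebo rate, and the effect on the contrast is smaller. The co-primary efficacy analyses are not touched. It is worth correcting before database lock because the error is avoidable and concerns the first exposure to study drug.

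**What to change.** In SAP 3.2, end the Part B period immediately before the date and time of the first Part C injection and start Part C at that injection, so that the periods are mutually exclusive. In 5.7.1, assign events with onset on that date by onset time relative to dosing. Pre-specify a default for a missing onset time, for example Part C unless the event is recorded as related to the pre-dose endoscopy (protocol 9.5.2 already collects relatedness to procedures), and add a sensitivity tabulation under the opposite assignment.

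The cost is a few lines of SAP text, a small change to the event-classification program and one extra table. The downside is that a few unrelated pre-dose events with no recorded time may be assigned to Part C; the sensitivity tabulation shows how much that matters. SAP 4.3 uses the same periods for concomitant medications and procedures, so the amendment should say whether the new boundary applies there too.
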